7.3.1. Collagen X

Collagen X Marker (CXM), is a degradation by-product of endochondral ossification that is released into the circulation in proportion to overall growth plate activity. This marker corresponds to the rate of linear bone growth at time of measurement as recently demonstrated in children of normal average growth. Serum concentrations of CXM plotted against age showed a pattern similar to well-established height growth velocity curves and correlated with height growth velocity calculated from incremental height measurements in this study (Coghlan 2017, Olney 2012).^{8,9} This study will be the first time the CXM will be studied in the achondroplasia population. The study will provide important new data to understand the circulating levels of a chondrocytic differentiation marker in children with achondroplasia.

7.3.2. CNP/proCNP

C-type natriuretic peptide (CNP) and its amino-terminal propeptide (proCNP) are known biomarkers for chondrocyte activity related to growth (Olney 2012)⁹ and have been shown to be expressed in elevated levels in children with achondroplasia suggesting a desensitization to CNP/proCNP in this population (Olney 2015).¹⁰ Only very limited longitudinal CNP/proCNP data are available in children with achondroplasia. This study will generate data to confirm and support the earlier finding. Our interest to understand the mechanism of achondroplasia requires that we establish additional data on the levels of CNP/proCNP in achondroplasia children of different ages. This data will provide further insight into the pathophysiology of the condition and help to understand whether the CNP/natriuretic peptide receptor B(NPRB) pathway contributes to the regulation of linear bone growth in achondroplasia children.

7.3.3. Additional Bloods Biomarkers

Additional biomarkers such as P1NP and CTX will be analysed. These analyses will be limited to biomarkers known to be related to bone growth, potential markers for treatment response or to the pathology of Achondroplasia.

CTX-1 is a crosslink peptide sequence of type I collagen, found, among other tissues, in bone. This specific peptide sequence relates to bone turnover because it is the portion that is cleaved by osteoclasts during bone resorption, and its serum levels are therefore proportional to osteoclastic activity.

P1NP is derived from type I procollagen cleavage during collagen synthesis and is a widely used bone formation marker representing osteoblast activity. Both markers are included in the ongoing Pfizer Achondroplasia Natural History studies and are strong candidate biomarkers to measure the efficacy of recifercept treatment in particular on bone growth.

7.4. Physical Activity Assessments

Physical activity assessments will be collected using wrist and lumbar sensors and will provide data to support assessment of daily activity and gait characteristics in children with achondroplasia. This may support future trial endpoints around daily functioning.

8. RESEARCH METHODS

8.1. Study Design

This is a prospective, registry study, to be conducted at multiple clinical centers globally, in which participants with achondroplasia will be followed over a five-year period with respect to achondroplasia symptoms, tests & treatments, anthropometric parameters and biomarkers of bone growth collagen X, CNP/proCNP, CTX and P1NP. No study drug will be administered, and no other type of therapy will be provided.

There will be a Screening visit, a Baseline visit, 3-month interval visits (± 3 weeks) including an annual visit every 12 months and an end of study visit. The end of study visit will be scheduled (or a given visit will be considered the end of study visit) as soon as any of the following criteria is met:

- Growth plates are considered to have fused, defined as standing height gain less than 1 cm within the last 6 months;
- The participant has reached end of puberty (Tanner Stage V);
- The participant is enrolled in any interventional study;
- The participant is diagnosed or develops any of the conditions related to exclusion criteria 1, 2 & 6;
- The participant is to receive any growth hormone, insulin-like growth factor 1 (IGF-1), anabolic steroids, or any other drug expected to affect growth velocity;
- The participant has participated in the study for 5 years;

- The participant is considered lost to follow-up.

The end of this study is defined as the date of the last visit of the last child participating in the study.

The study will enroll participants in the following approximate proportions:

- 40% 0-5y;
- 40% 5-10y;
- 20% 10-15y.

Any treatment received during the study in relation to important medical events and any treatment based on the medical judgment of the investigator that may affect the participant's growth trajectory must be recorded in the eCRF:

- Description of the treatment (for medical treatment: route of administration, frequency and dose);
- Indication;
- Start and stop date.

Treatment is defined as any medical, surgical or other intervention to treat the underlying condition.

The rationale for the study design is summarised as follows:

A prospective longitudinal design is selected to collect blood samples and anthropometric data simultaneously in a standardized fashion, and thereby allowing for estimation of between and within participant variability laboratory parameters as well as testing for possible correlations between laboratory parameters and growth.

A five-year data collection period is chosen to allow detection of substantial growth as measured by the anthropometric endpoints, in order to enhance the strength of a possible correlation.

Fasting prior to blood sampling is required to avoid variability due to impact of the digestive process on circulating levels of metabolic proteins related to bone growth. The fluctuation in bone metabolism markers after eating has been documented in other studies.

The age range 0 - 15 years is chosen to provide a broad knowledge of the serum-levels of collagen X during different stages of growth in childhood.

Information on Tanner Stage of Puberty will be collected in participants at 7 years of age and above to capture signs of initiation of puberty, which may affect growth.

Laboratory assays will be applied for the analysis of collagen X & other associated biomarkers based on venous blood draws.

Health related quality of life measures will be collected to provide information about the quality of life of children, families and caregivers of children with achondroplasia.

Physical activity monitoring will be collected in participants at 2 years of age and above to capture activities of daily living ‘in the real world’ by using digital accelerometry sensors.

8.1.1. Inclusion Criteria

Participants must meet all the following inclusion criteria to be eligible for inclusion in the study:

1. Written informed consent/assent is obtained from the participant and/or parent(s)/legal guardian(s) before any study-related activity is carried out.
2. The participant/parent(s)/legal guardian(s) is able to provide written informed assent, where this is required according to national legislation, before any study-related activity is carried out.
3. The participant has been diagnosed as having achondroplasia documented by clinical diagnosis.
4. The participant is between 0 years and 15 years of age, up to day before 15th birthday, on the date of consent/assent.
5. The investigator has considered the family and prospective participating participant being able to comply with the study procedures.

Evidence of a personally signed and dated informed consent/assent document indicating that the participant (or a legally acceptable representative) has been informed of all pertinent aspects of the study.

Participants who are willing and able to comply with scheduled visits, laboratory tests and other study procedures.

8.1.2. Exclusion Criteria

Participants meeting any of the following criteria will not be included in the study:

1. The participant has a diagnosis of hypochondroplasia or any short stature condition other than achondroplasia (eg, spondyloepiphyseal dysplasia congenital [SEDC], pseudo-achondroplasia, trisomy 21).
2. The participant has any medical condition that may impact growth or where the treatment is known to impact growth, such as but not limited to hypothyroidism or hyperthyroidism, insulin-requiring diabetes mellitus, autoimmune inflammatory disease (including celiac disease, lupus [SLE], juvenile dermatomyositis, scleroderma, and others), autonomic neuropathy or inflammatory bowel disease.
3. Treatment in the previous 12 months prior to consent/assent with growth hormone, insulin-like growth factor 1 (IGF-1), anabolic steroids, or any other drug expected to affect growth velocity.
4. Any surgery that affects the growth plate of the long bones that is planned, or has occurred in the past 18 months.
5. Participation in any interventional study (investigational product or device) for treatment of achondroplasia or short stature.
6. Has had bone-related surgery impacting assessment of anthropometric measurements or is expected to have it during the study period. Participants with previous limb-lengthening surgery may enroll if surgery occurred at least 18 months prior to the date of consent/assent and healing is complete without sequelae as determined by the investigator.
7. Has any condition or circumstance that in the view of the investigator places the child at high risk of poor compliance with the visit schedule or of not completing the study.
8. Any concurrent disease or condition that, in the view of the investigator, would interfere with study participation.

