STUDY DURATION	
The overall study period is foreseen to be 5 years.
 
The participant may continue study participation until any of the following criteria is met:
 
• Growth plates are considered to have fused, defined as standing height gain less than 1 cm within the last 6 months;• The participant has reached end of puberty (Tanner Stage V);• The participant is enrolled in any interventional study;• The participant is diagnosed or develops any of the conditions related to exclusion criteria 1, 2 & 6;• The participant is to receive any growth hormone, insulin-like growth factor 1 (IGF-1), anabolic steroids, or any other drug expected to affect growth velocity;• The participant has participated in the study for 5 years;• The participant is considered lost to follow-up.

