7. RESEARCH QUESTION AND OBJECTIVES

Primary Objective(s):	Primary Endpoint(s):

 Collection of longitudinal anthropometric and disease-related complication data in children with achondroplasia. 	Standing height, sitting height, knee height, head circumference, arm span, length of the legs (calculated as the difference between standing and sitting height) and achondroplasia related AEs.
Secondary Objective(s):	Secondary Endpoint(s):

 Investigation of potential serum biomarkers in children with achondroplasia. 	
 Baseline and post-baseline measurements of serum collagen X marker.
CCI [REDACTED]	[REDACTED]
[REDACTED]	[REDACTED]
[REDACTED]	[REDACTED]

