9.8.3. Orthopaedic Complications

- Imaging of the bones or knees.
- Tibial bowing including the dates of any surgery for.
 - Osteotomy.
 - 8-plates.
- Kyphoscoliosis including the presence of wedging on imaging and need for surgery.
- Lumbar lordosis.
 - Diagnosis of lordosis.
 - Presence of neurological signs in legs.
 - Impaired walking.

- Any surgical intervention.

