Data following procedures or treatments that may affect growth velocity will be excluded from the analysis of anthropometric parameters.

Subgroup analysis should be made by gender, age groups, and the combination of gender and age group.

Biomarker **CCI** will be described in a separate SAP and presented separately from the main CSR.

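### Ending participation for on-study bone surgery that affects anthropometric assessment cuts off complication follow-up, a primary-objective outcome to which that exit is related

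*Protocol*

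**What the plan says.** **Exit rule.** Protocol Section 8.1 schedules the end of study visit "as soon as any of the following criteria is met". One of the criteria is "The participant is diagnosed or develops any of the conditions related to exclusion criteria 1, 2 & 6". The Study Duration entry of the Section 3 summary repeats the list under "The participant may continue study participation until any of the following criteria is met". Criterion 6 in Section 8.1.2 reads "Has had bone-related surgery impacting assessment of anthropometric measurements or is expected to have it during the study period".

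**Outcome.** The primary objective in Section 7 is "Collection of longitudinal anthropometric and disease-related complication data in children with achondroplasia", and the primary endpoints include "achondroplasia related AEs". Section 9.8 has complications recorded at baseline and throughout the study. Among the orthopaedic items in Section 9.8.3 is "Tibial bowing including the dates of any surgery for", followed by osteotomy and 8-plates. Need for surgery in kyphoscoliosis and surgical intervention for lumbar lordosis are also listed. Under Section 9.6.1, follow-up of symptoms and of treatment outcome runs only until the child's participation ends.

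**Analysis.** Section 11.5 states: "Data following procedures or treatments that may affect growth velocity will be excluded from the analysis of anthropometric parameters". SAP Section 5 has an equivalent rule, and the SAP plans a listing of these exclusions (16.2.3.1). SAP Section 9.1 summarises achondroplasia-related symptoms, tests and treatments as counts and percentages of children. The list of reasons for leaving in SAP Section 3 covers growth-plate fusion, Tanner Stage V, interventional study enrolment, 5 years and loss to follow-up. It has no trigger for criteria 1, 2 and 6.

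**The concern.** The registry sets out to describe complications over time, including orthopaedic ones and their surgical treatment. Yet a child whose orthopaedic disease leads to a qualifying operation leaves the registry because of it. Follow-up for the complication part of the primary objective then stops for a reason related to the outcome being measured. Censoring of that kind is informative.

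The loss goes beyond orthopaedics. Once participation ends, later respiratory, neurological and ear complications in that child are not collected either. A crude percentage that keeps the child in the denominator, but stops looking early, tends to be too low. If the registry is used as a reference for future trials, as Section 11.5 intends, the complication burden carried forward could be understated.

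**Working it through.** The point rests on the text. The documents give no surgery rate or dropout rate, so there is no planned figure to reproduce.

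**Step 1. What is kept and what is lost at exit.**

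| Item | Captured? | Basis |
|---|---|---|
| Qualifying operation already done, with date | Can be | Complications, tests and treatments are collected at the End of Study visit (Protocol Sections 5 and 8.1.3) |
| Operation only expected at exit | Not if it takes place after exit | No collection after participation ends |
| Outcome of the operation | Not after exit | Section 9.6.1 |
| Repeat surgery | No | Same |
| Any later complication of any type | No | Same |

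The second row depends on reading the exit rule together with criterion 6. Criterion 6 covers surgery that is expected, and the exit rule refers to conditions related to that criterion. On a plain reading, expectation alone is enough, although Section 8.1 does not say so outright.

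**Step 2. Do the rules fit together?** The exclusion rule in Protocol Section 11.5 and SAP Section 5 has work to do only if some data are collected after a growth-affecting procedure. The exit rule removes children at a closely related point. The SAP list of reasons for leaving lacks the trigger altogether. The SAP states that it was written for protocol version 2.0, whereas the latest entry in the protocol's document history is version 3.0. Whatever the reason, the two documents do not agree on who stays in.

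**Step 3. Illustration of exits (assumed rates).** Take about 300 children (Protocol Section 3), 5 years at most, a constant yearly rate h of qualifying surgery and no other exits.

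- Share ended by year 5 = 1 − exp(−5h)
- Child-years observed = 300 × [1 − exp(−5h)] / h, out of 300 × 5 = 1500

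| h per year | Ended by year 5 | Children | Child-years observed | Lost |
|---|---|---|---|---|
| 1% | 4.9% | 15 | 1463 | 2.5% |
| 2% | 9.5% | 29 | 1427 | 4.8% |
| 5% | 22.1% | 66 | 1327 | 11.5% |
| 10% | 39.3% | 118 | 1180 | 21.3% |

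Other exits would shorten follow-up anyway, so the loss due to this rule alone would be smaller than shown.

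**Step 4. Illustration of the effect on a crude percentage (assumed inputs).** Take another complication occurring at 0.10 per year in children without surgery and at m = 0.10 × R per year in children with surgery. Let surgery time be uniform over 5 years, with exit at surgery.

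- True 5-year risk in a child with surgery: 1 − exp(−5m)
- Observed before exit: 1 − [1 − exp(−5m)] / (5m)
- Shortfall in the overall percentage = share with surgery × (true − observed)

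| R | True, child with surgery | Observed | Shortfall if 10% have surgery | 20% | 30% |
|---|---|---|---|---|---|
| 1 | 39.3% | 21.3% | 1.8 points | 3.6 | 5.4 |
| 2 | 63.2% | 36.8% | 2.6 points | 5.3 | 7.9 |
| 3 | 77.7% | 48.2% | 2.9 points | 5.9 | 8.8 |

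For 20% with surgery and R = 2, the true overall figure is 0.8 × 39.3% + 0.2 × 63.2% = 44.1%. The crude figure is 0.8 × 39.3% + 0.2 × 36.8% = 38.8%. At R = 1 the shortfall comes from shorter observation alone, and reporting per person-time would remove it. At R above 1, person-time removes only part of it.

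**The case against.** The best defence is that the registry mainly supplies reference data for future interventional studies (Section 11.5). Leaving out children whose body dimensions have been surgically altered fits that purpose. For the anthropometric half of the objective this stands. It does not explain why complication data should stop too. The only reason given for the termination criteria, in Section 6, concerns fused growth plates and eligibility for later trials.

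Several stronger readings are tempting, and the documents do not support them:

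- **That any bone surgery ends participation.** Criterion 6 is limited to surgery that interferes with anthropometric assessment. The protocol does not say which operations in Section 9.8.3 qualify.
- **That the exit adds no protection to growth data.** The rule in Section 11.5 concerns growth velocity, and SAP Section 5 concerns height growth. An operation could distort a measurement without changing growth, and those rules would not clearly remove the distorted values.
- **That surgery disappears from the record.** An operation already done can be captured at the End of Study visit, and SAP Section 7.1 already tabulates reasons for discontinuation.
- **That growth-plate surgery is shown to be treated inconsistently.** Criterion 4 is not an exit trigger, but criterion 6 may be broad enough to cover such surgery when it affects measurement. The documents do not classify 8-plates as growth-plate surgery.
- **That the children lost are the most affected.** This is plausible, but no passage states it. Section 6 places the severe respiratory and neurological complications in the youngest children and does not link them to orthopaedic surgery.

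**Conclusion.** The point holds in a limited form. The exit rule stops complication follow-up for a reason related to the complications under study. What is lost is any operation still only expected at exit, the later outcome of surgery, repeat operations and all subsequent complications. A first operation already done need not be lost. The crude percentages in SAP Section 9.1 would tend to understate cumulative burden.

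The direction rests on two things in the documents: no collection after participation ends, and percentages without person-time. The size cannot be determined, because every rate in the working is an assumption. Across the assumed inputs the shortfall in a crude percentage runs from about 2 to about 9 points. Separately, the protocol and SAP disagree on whether this trigger exists, and that needs reconciling whatever the size.

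**What to change.** **Preferred change.** For criterion 6 surgery arising on study, separate the end of anthropometric analysis from the end of complication collection:

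1. Exclude later anthropometric data from analysis. Extend the rule in Protocol Section 11.5 and SAP Section 5 to procedures that affect anthropometric assessment as well as growth velocity.
2. Continue collecting complications, tests and treatments to 5 years, for example from medical records, which Section 8.1.3 already names as their source.
3. Align the Study Duration entry in Protocol Section 3, Protocol Section 8.1 and SAP Section 3. State which operations count, whether expectation alone counts, and whether criterion 4 surgery is handled in the same way.

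**If the exit is kept.** Report complications per person-time as well as in percentages. Tabulate surgery-related exits separately, split into done and expected. State that the loss of follow-up is informative and that person-time does not fully correct for it. Do not count an expected operation as an event, since it may never take place.

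**Cost.** The preferred change alters when participation ends, so it is a protocol amendment needing ethics approval (Section 14.3), with continued data collection for a limited number of children. It adds no new procedure. The fallback analyses need only SAP wording, though the disagreement between the protocol and SAP lists would still have to be resolved.

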8.1.3. Variables

Variable	Role	Data source(s)	Operational definition
Anthropometric Measurements	Analysis of growth parameters	Anthropometric measurements	Collection every 3 months & End of Study
Tanner Staging	Assess stage of sexual development	Physical Examination	Collection every 3 months & End of Study
Achondroplasia related complications, tests & treatments	Characterize treatments for Achondroplasia	Medical Records	Collection every 3 months & End of Study
Non-Achondroplasia	Characterize medical	Medical records	Collection every 3 months

Variable	Role	Data source(s)	Operational definition
co-morbidities and treatments	history		& End of Study
Biomarker Blood Sample	Analysis for potential biomarkers of bone growth	Blood sample	Blood sample every 12 months & End of Study
Activity Tracker & Gait Measurement	Analysis of daily activity & gait when walking	Activity Tracker & Gait Mat	Collection every 3 months & End of Study
Quality of Life	Assess Quality of Life in Participant & families with Achondroplasia	Questionnaire	Collection every 3 months & End of Study

8.1.3.1. Data Sources

Source documents provide evidence for the existence of the participating child and substantiate the integrity of the data collected. Source documents are filed at the investigator's study site.

Data entered in the eCRF that are transcribed from source documents must be consistent with the source documents and the discrepancies must be explained. The investigator may need to request medical records from other healthcare professionals, if appropriate. Also, current medical records must be available. The use of electronic source data is described in FDA, EU Chinese and Japanese Guidance for Industry – Electronic Source Data in Clinical Investigations (2013).

All study data must be verifiable by source documents. Additionally, the following data entered into the eCRF, should be verifiable by source documents in the participant's medical record, or other records, at the study site, as applicable:

- Details of study participation (study ID and unique identifier);
- Date(s) of informed consent of parent(s)/legal guardian(s);
- Date of informed assent of participant;
- Date of each study visit including signature and/or initials of person(s) conducting the study visit;
- The participant's date of birth, or – as per local regulations – the month and year of birth relative to the date of the signing of consent/assent;
- Confirmation by genetic testing, documenting the diagnosis of achondroplasia;
- Results of anthropometric measurements.

Information recorded in the eCRF system should be supported by corresponding source documentation. Examples of acceptable source documentation include, but are not limited to, hospital records, clinic and office charts, laboratory notes, and recorded data from automated instruments, and memoranda.

Clinical laboratory data for the biomarkers required by the protocol will be electronically transferred from the central laboratory to the sponsor or its designee.

Confirmation of genetic testing should be available as source documents from the local laboratory when the testing is performed. Results should be available and recorded in the eCRF prior to the end of study visit.

